### **3.2 Comparator Devices: mylife™ OmniPod® Insulin Management System and Other Study Devices**

#### **3.2.1 Multiple daily injection therapy**

Intensified therapy, either MDI or CSII, strongly depends on multiple self-monitored blood glucose values. Both the mylife™ OmniPod® and the Accu-Chek® Solo micropump system offer an integrated blood glucose meter. Accordingly, subjects on CSII therapy will use the meter integrated into the respective pump system. Subjects in the MDI control arm will use either a blood glucometer of their own choice, if this is listed as a compatible meter with Accu-Chek® Smart Pix or will switch to a provided Accu-Chek® Aviva/Performa Connect or Accu-Chek® Aviva/Performa Nano as blood glucose meter for the duration of the study. No effect is expected by the specific brand or model of blood glucose meter.

Figure 5: Accu-Chek® blood glucose meters

Subjects in group A will use either a Smart Pix compatible blood glucometer of their own choice or the depicted device (Accu-Chek® Aviva/Performa Connect, left or Accu-Chek® Aviva/Performa Nano, right) for 26 weeks.

MDI therapy has been chosen as comparator, as it is standard of care.

#### **3.2.2 mylife™ OmniPod® Insulin Management System**

The mylife™ OmniPod® Insulin Management System is a patch pump system designed by Insulet Corporation. It was first brought to the US market and is available worldwide (including UK and Germany) since 2010 under the brand name mylife™ OmniPod®.

[figure not shown]

Figure 6: mylife™ OmniPod® Pod (left top), mylife™ OmniPod® infusion set (left bottom) and mylife™ OmniPod® Personal Diabetes Manager (right)

The mylife™ OmniPod® Insulin Management System is comprised of two components: the actual Pod and a Personal Diabetes Manager (PDM) that serves as remote control of the pod.

The Pod is single-use disposable, microprocessor-controlled infusion pump that is worn directly on the body. The adhesive on the base of the Pod keeps it in place for the typical wear times of 48 to 72 hours.

The PDM is a hand-held, battery-powered device integrating a blood glucose (BG) meter that remotely controls the insulin delivery of the pod. BG and insulin therapy data are stored and can be displayed directly on the PDM. In addition, the PDM provides further information on audio alarms, alerts, and reminders related to insulin delivery, reservoir level, Pod functioning, and battery life.

The Pod incorporates an insulin reservoir holding up to 2 ml (i.e. 200 units of U100 insulin) which has to be filled by the user with equipment provided with each Pod (fill syringe and needle). A separate infusion set or reservoir is not needed. Insulin is delivered through a soft cannula integrated in the Pod and inserted automatically into the subcutaneous tissue at an angle of 45°.

All components of the mylife™ OmniPod® diabetes management system used in the study will have CE marking.

Subjects in group C will use this device for 26 weeks.

This device has been chosen as comparator, as it is the only patch pump available on the market so far and therefore defines the class of patch pumps.

For the time of mylife™ OmniPod® use during the study, the Sponsor will cover the costs for the mylife™ OmniPod® Insulin Management System.

### 3.2.3 Other devices

Subjects using a flash or real-time continuous blood glucose measuring device may continue to use it.

Apart from the devices described above, all subjects using a blood glucometer will need a lancing device. As no effect on the study results is expected from the specific type of lancing device used, subjects may use the lancing device they prefer. The Accu-Chek® FastClix lancing device is included in the starter packed of the Accu-Chek® Solo system.

For purposes of downloading BG data, data from mylife™ Omnipod®, or data from the Accu-Chek® Solo micropump system, the Accu-Chek® Smart Pix software and corresponding Smart Pix device reader will be used by the study sites.

The Sponsor will provide the following materials to all investigators and participating centers:

- IEC approved study protocol
- Electronic Case Report Form (eCRF)
- IEC approved informed consent
- Investigator site file (ISF)
- Investigator/hospital contract
- Electronic subject questionnaires
- Accu-Chek® Smart Pix Software and Smart Pix Device Reader

### 3.3 Status of Documentation of Study Device(s)

The Accu-Chek® Solo micropump system will not have CE marking when the study starts. A manufacturer’s declaration will be provided. CE marking is expected to be available before the end of the study. On availability of CE mark, CE marked material will be usable in the study and will be handed out to the study subjects as appropriate. As the differences to the non-CE marked material are minor (mainly bug fixes), the effects on study outcomes are negligible.

All other devices have CE marking and marketed in countries of the European Union.

**Table 1: Regulatory status of the study devices**

Device Name	CE marking at study start
Accu-Chek® Solo Aviva/Performa Diabetes Manager (Version PPB 2/FC 2.3)	No
Accu-Chek® Solo pump base (Version PPB 1/V 1.00 and PPB 2/V 1.02)	No
Accu-Chek® Solo insulin reservoir (Version PPB G3)	No
Accu-Chek® Solo infusion set assembly (Version PPB G3)	No
Accu-Chek® Solo inserter (Version PPB 2)	No
mylife™ OmniPod®	Yes
Accu-Chek® Aviva/Performa Connect 	Yes
Accu-Chek® Aviva/Performa Nano 	Yes

 Not in Poland

 In Poland only

CONFIDENTIAL

Accu-Chek® FastClix lancing device 	Yes
Accu-Chek® SoftClix lancing device 	Yes

---

 Not in Austria

 In Austria only

## 4 Study Objectives

### 4.1 Primary Objective

The primary objective of this study is to compare treatment satisfaction with Accu-Chek® Solo system vs. MDI and versus mylife™ OmniPod®, measured by the difference in the Diabetes Technology Questionnaire (DTQ) change score after 26 weeks.

The two comparisons will be performed using a hierarchical procedure. First, the comparison between the Accu-Chek® Solo system vs. MDI will be performed and only if the corresponding Null hypothesis of no difference between both systems can be rejected, the second comparison between Accu-Chek® Solo system and versus mylife™ OmniPod® will also be performed.

### 4.2 Secondary Objectives

The secondary objectives of this study are to evaluate:

- Psychological parameters that describe or affect therapy:
  - Diabetes-related Emotional Distress assessed by PAID-5.
  - Device satisfaction
  - Device and Treatment Preference
- Physical parameters that describe therapy changes or success:
  - HbA1c
  - Change in weight and BMI
  - glycemic variability
- Therapy parameters that describe therapy changes or may affect the results
  - Indication for commencement of CSII
  - Type of insulin used
  - Total daily insulin dose (TDD)
  - Total daily basal insulin dose (TBD)
  - Average number of SMBGs per day
  - Frequency of hypoglycemic events
  - Frequency of hyperglycemia
  - Frequency of consultations between scheduled visits, emergency and call center calls, hospitalizations and absenteeism from work/school
- Device specific parameters that may affect user acceptance
  - number of pods/ infusion assemblies falling off prematurely
  - average infusion assembly usage time
  - number, type and intensity of skin reactions
- Parameters that may affect socio-economic acceptance
  - Insulin amount left in device at reservoir change / device discard

CONFIDENTIAL

- Amount of waste, inferred by total material consumption

## **5 Subject Selection**

Subjects will be identified and recruited from the Investigator's established subject population or from respective group practices using the inclusion/exclusion criteria; see Section 6.1 and Section 6.2.

If a subject agrees to consider participation in the study, he/she shall be informed (verbally and in writing by means of the Subject Information Leaflet) and given the possibility to ask questions to authorized study staff. If a subject decides to participate, he/she shall sign the current Ethics Committee (EC) approved Subject Informed Consent Form before any study-related procedures; see Section 12.2.

During the Screening and Baseline Visits, the subject will be interviewed to obtain demographic information and diabetes and other medical history to determine if he/she meets all of the inclusion, but none of the exclusion criteria.

## 6 Study Population

A total of 180 adult patients with type 1 diabetes suitable for CSII therapy will be included, if they comply with the following inclusion and exclusion criteria.

### 6.1 Inclusion Criteria

To be eligible to participate in this clinical study, subjects must meet **ALL** of the following criteria:

- Signed written Informed Consent
- Diagnosed type 1 diabetes mellitus
- At least 6 months experience with MDI therapy
- Age  $\geq 18$  years and age  $\leq 65$
- Able to perform carbohydrate counting
- Clinically suitable for CSII including willingness to measure blood glucose at least 4 times per day or to use flash or real-time continuous glucose monitoring consistently
- HbA1c between 7.5% (58 mmol/mol) and 9.0% (75 mmol/mol) (determined within the last 2 months)
- Ability and willingness to read and understand study materials (subject information, data protection and written consent form, all questionnaires etc.) and to comply with study procedures
- Ability and willingness to use investigational devices independently and respond to alarms after training and run-in phase
- Using a BG-meter or real-time continuous glucose monitoring device that can be downloaded via Accu-Chek® Smart Pix or willingness to use a compatible meter that will be provided for the duration of the study

### 6.2 Exclusion Criteria

Subjects may not participate in this clinical study if they meet **ANY** of the following criteria:

- Prior insulin pump use
- Relevantly impaired hypoglycemia awareness
- History of  $>1$  hospitalization due to severe hypoglycemia within the previous 3 months
- History of  $>1$  hospitalization due diabetic ketoacidosis within the last 3 months
- Significant manifestation of diabetes-related late complications
- Pregnant or planning to become pregnant or breastfeeding
- Known allergic reactions to plaster adhesive
- Chronic use (therapy lasting for more than 3 months) of
  - steroids in adrenal suppressive doses,
  - immunosuppressive medication, or
  - chemotherapy
- Serious or unstable chronic medical or psychological condition(s)
- Addiction to alcohol or other substance(s) of abuse as determined by the investigator
- Psychological condition rendering the subject unable to understand the nature and the scope of the study
- Plans for relocation or extensive travel
- Participation in another clinical study within 4 weeks prior to the screening visit
- Dependency on Sponsor or Investigator (e.g. co-worker or family member)

### **6.3 Point of Enrolment and Withdrawal**

A subject is considered enrolled in the study:

- as soon as he/she has signed the Subject Informed Consent Form and has been deemed eligible according to above inclusion/exclusion criteria.

A subject is considered withdrawn if he/she was first enrolled, and thereafter one or more of the following occurs:

- Withdrawal of consent to participate in the study.
- Non-compliance with the protocol procedures e.g., subject missed two consecutive study visits and/or one period with the study device(s).
- Subject requires chronic steroid in adrenal suppressive doses, other immuno-modulatory medication or chemotherapy being determined after having been enrolled.
- Subject becomes pregnant (self-reported).
- Investigator determines it is not in the best interest of the subject to continue participation in the study.

If any of the above occurs, the Investigator will:

- Ask the subject to present at site in order to ensure complete documentation (eCRF and electronic questionnaires), and to return all study materials.
- Complete the Study Completion Form in the eCRF including the date of and reason for early discontinuation.

If withdrawal occurs after completion of visit 2:

- Ask the subject to perform visit 5 as early termination visit

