### 11.2 Populations for Analysis

The safety population consists of all subjects enrolled.

The primary analysis population will be the Full Analysis Set (FAS). The FAS is defined as all randomized subjects.

The per protocol population (PP) consists of all subjects who have completed all visits according to the protocol. Detailed criteria for assignment to the PP population will be described in the SAP.

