### **11.3 Handling of subject withdrawals and missing values**

As described in 11.2, all randomized subjects will be part of the FAS group and thus be utilized for primary analysis. The pink (left) part of the DTQ will be assessed before randomization. This will guarantee that no bias will be introduced by a possible preference of subjects for a particular group, resulting in a possible withdrawal of individual subjects right after randomization.

For subjects that answered DTQ during Visit 4, these answers will be used for the primary analysis.

The following steps are planned to avoid missing data:

- In case of withdrawal, subjects will be asked to answer the DTQ questionnaire during the End of Study visit.
- If it will not be possible to get questionnaire results at the End of Study visit but questionnaire results are available from week 13 (visit 3), these results will be used, i.e. a LOCF procedure will be applied.
- If there will be no results from week 13, e.g. because a subject will withdraw before week 13, a value of 3 (“Same”) will be imputed as the answer to every individual question. This will result in a total score of 90 (30 times 3), which corresponds to the assumed mean result for the MDI group and thus represents a conservative imputation (the anticipated mean score for the Accu-Chek® Solo group is 110).

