## 2.10. Populations for Analysis

Due to the design of the study with a parallel phase between visits 1 and 4 and a one-armed phase in which all subjects will use the Accu-Chek® Solo micropump system, analysis will distinguish between these phases. Wherever appropriate, the treatment arm, to which a subject is randomized, will be denoted as “arm”, the current treatment as “trt” in listings and tables. E.g., a subject randomized to treatment arm B (MDI) will therefore have the analysis assignments B for both, arm and trt between visits 1 and 4, while the corresponding assignments will be B as arm and A as trt between visits 4 and 5.

The following populations are defined for analysis:

- The safety population (SP) is defined as all enrolled patients with data documented at at least one of the visits 1 to 5.
- The full analysis population (FAS) will follow the intention to treat principle, i.e., all subjects will be analyzed according to the treatment arm they are randomized to..
- The per-protocol (PP) population will be defined on a per visit basis. For a given visit, it will include all subjects that will have completed this visit and have no severe protocol deviations.

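### Protocol 6.3 counts a missed, undefined period with the study device as study withdrawal, so subjects removed before week 26 have no scheduled Visit 4 DTQ or HbA1c

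*Protocol*

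**What the plan says.** Protocol 6.3 lists the events after which an enrolled subject counts as withdrawn. One of them is "Non-compliance with the protocol procedures e.g., subject missed two consecutive study visits and/or one period with the study device(s". Neither document says what a period is; elsewhere they speak of phases.

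For every withdrawal the investigator is to "Ask the subject to present at site in order to ensure complete documentation (eCRF and electronic questionnaires), and to return all study materials" and to complete the Study Completion Form. After Visit 2 there is one further instruction: "Ask the subject to perform visit 5 as early termination visit". Nothing asks the subject to return at week 26.

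The analysis is built on week 26. Protocol 4.1 defines the primary measure as the difference in the "Diabetes Technology Questionnaire (DTQ) change score after 26 weeks". Protocol 11.2 states: "The FAS is defined as all randomized subjects". SAP 2.10 says that this population "will follow the intention to treat principle, i.e., all subjects will be analyzed according to the treatment arm" to which they were randomized.

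Protocol 11.3 and SAP 3.4.1 set an order of substitutes when there is no Visit 4 DTQ:

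- First, "In case of withdrawal, subjects will be asked to answer the DTQ questionnaire during the End of Study visit". The SAP stores this score among the Visit 5 variables and copies it from there.
- Failing that, for a week-13 questionnaire, "these results will be used, i.e. a LOCF procedure will be applied".
- Failing both, every item is set to 3, a total of 90, which both documents call conservative.

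**The concern.** An intention-to-treat comparison at week 26 needs the week-26 outcome of each randomized subject, whether or not the device is still in use. Section 6.3 makes no distinction between stopping the device and leaving the study. For subjects removed under this rule before Visit 4, the plan itself ensures that the outcome is not observed, even if they would have been willing to give it.

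The endpoint is treatment satisfaction, so giving up the device is closely tied to it. Protocol 11.5 describes MDI participation as no change of treatment, so rejection of a newly assigned device is more likely in arms A and C. Protocol 1.1 adds that Solo needs more handling steps and that this may affect acceptance, so arms A and C may differ as well. The HbA1c endpoint in SAP 6.8.1.2, Visit 4 minus Visit 2, has the same gap.

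The existing checks do not recover these values. The per-protocol run (SAP 6.2, with 2.10) keeps only subjects who completed the visit, so it drops the same people. The Fisher test (SAP 6.11) compares withdrawal rates; equal rates with different reasons would pass it.

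**Working it through.** **1. The plan's own figures.** Inputs from Protocol 11.1: means 110 and 90 (difference 20), SD 30, two-sided alpha 0.05, power 90%, drop-out up to 18%.

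- Normal approximation: n = 2 × (1.960 + 1.282)² × 30² / 20² = 47.3, so 48 per group.
- Exact two-sample t-test: power 0.898 at 48 and 0.904 at 49, so 49, as stated.
- Enrolment: 49 / 0.82 = 59.8, so 60 per arm, as stated.

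Neither figure is in dispute. The 18% covers drop-out for any cause (0.18 × 60 = 10.8 subjects per arm). It is not a rate of stopping the device.

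**2. What a subject withdrawn between Visits 2 and 4 contributes.**

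| Item | Scheduled at week 26? | Value used instead |
|---|---|---|
| DTQ change score | No | Early-termination score, else week 13, else 90 |
| HbA1c | No | Drawn at early termination (Protocol 7.6); SAP 3.4.4 carries forward other missing scores where applicable |

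The subject stays in the FAS, with a value that was not measured at week 26.

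**3. When 90 is conservative.** If all 18% of Solo subjects receive 90 and the rest average 110, the difference is 0.82 × 20 = 16.4, and power with 60 per arm is about 0.84. That works against Solo. It is conservative only if the missing subjects would have scored above 90.

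**4. Size of a possible shift.** Let p be the share of the Solo arm affected and g the gap, substituted score minus true week-26 score. The Solo mean shifts by p × g. Losses in the comparator arm shift its mean in the same way and are set to zero here. No value of g is given in the documents; 5, 15 and 30 points are assumptions.

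| p | gap of 5 | gap of 15 | gap of 30 |
|---|---|---|---|
| 18% | 0.9 | 2.7 | 5.4 |
| 9% (half of 18%) | 0.45 | 1.35 | 2.7 |
| 5% | 0.25 | 0.75 | 1.5 |

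**5. Sign.** Each case has p = 18%.

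- True week-26 score 75, given 90: 0.18 × (90 − 75) = +2.7, in favour of Solo.
- Early-termination score 75, but the subject is back on MDI and would answer 90 at week 26: 0.18 × (75 − 90) = −2.7, against Solo.
- Given 90 and would answer 90: 0.

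**6. Effect on the test.** With 60 per arm the standard error is 30 × √(2/60) = 5.48, so 2.7 points is 0.49 standard errors. If the true means are equal, the chance of a significant result in favour of Solo is Φ(0.49 − 1.96) = 7.1% with +2.7 and Φ(−0.49 − 1.96) = 0.7% with −2.7, against 2.5% nominal. If the true difference is 20, a shift of −2.7 leaves 17.3, and power falls from 0.95 to Φ(17.3/5.48 − 1.96) = 0.88. These are normal approximations without covariate adjustment.

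**The case against.** **The subjects' views are already sought and used.** A reader might infer that the least satisfied pump users never give the rating that counts, or that they leave the analysis. The documents do not support that. Protocol 6.3 asks withdrawn subjects for the questionnaires, Protocol 7.10 schedules the DTQ change part at Visit 5 in all arms, and Protocol 11.3 and SAP 3.4.1 use that score before any other substitute. A dissatisfied subject who keeps using the pump reaches Visit 4 as normal. This objection stands. What is missing is the week-26 value, not every value.

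**Bias in favour of Solo is not established.** A reader might also infer that 90 flatters Solo. The change item asks for a comparison with treatment before the study (SAP 2.5), which was MDI with no prior pump use (Protocol 6.1 and 6.2). A subject who has gone back to MDI may well answer near 90, the score that SAP 2.8 equates with no change. This stands too: the sign is open.

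**The imbalance between arms is not certain.** The rule refers to study devices, and SAP 3.5.4.2 counts MDI among them, so MDI subjects can also be withdrawn for non-compliance. Against OmniPod both arms use pumps and no direction can be given. Rejection of a newly assigned device remains more likely in the pump arms, but the documents give no rates.

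**The rule may seldom act.** If a period means the whole 26-week phase, few or no subjects would be removed before Visit 4. That is a further reason to define it, since sites could otherwise apply it differently.

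**Which score should be primary is a choice.** A score at stopping describes the device; a Visit 4 score describes the policy of assigning it. This stands and is why both should be reported.

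**Conclusion.** The point holds in a limited form. Protocol 6.3 merges stopping the device with leaving the study. For subjects removed on that ground before week 26, it leaves no scheduled Visit 4 DTQ or HbA1c, against the plan's own intention-to-treat aim. The substituted values can bias the comparison, but the documents settle neither how much nor in which direction.

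As a guide to scale, 2.7 points either way on a planned effect of 20 rests on two assumptions: that the full all-cause allowance of 18% is affected, and that the gap is 15 points. At 5% affected and the same gap the shift is 0.75 points. Subjects who supply an early-termination score close to their week-26 view add little.

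The stronger readings, that dissatisfied users are lost to the analysis or that Solo is bound to gain, should not be drawn. The change is worth making because it is cheap and replaces an unknown with data.

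**What to change.** - **Protocol 6.3:** define the period, and list stopping the assigned device separately from withdrawing from the study. No treatment decision changes; only follow-up does.
- **Data collection:** ask subjects who stop the device and still consent to complete the DTQ at stopping, then to attend the already scheduled Visit 4 for DTQ and central HbA1c.
- **Primary analysis:** use the Visit 4 DTQ in the FAS, as Protocol 11.3 and SAP 3.4.1 already do when it exists. Report beside it an analysis using the at-stopping DTQ, because an answer given after return to MDI may not reflect the device.
- **Sensitivity analysis in the SAP:** for pump-arm subjects who would otherwise be given 90, repeat the primary analysis with lower values, for example 85, 75 and 60, and state whether the conclusion changes.

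The cost is a protocol amendment, a line in the consent form, some follow-up effort and a short SAP addition. No new week-26 visit is needed. Some subjects will still decline, so the substitution rules remain necessary for them.
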